6.2 DETAILS OF TRIAL PROCEDURES AT SELECTED VISITS

6.2.1 Screening period

After having been informed about the trial, all subjects will provide written informed consent in accordance with GCP and local legislation prior to enrolment in the study. For information regarding laboratory tests (including drug and virus screening), ECG, vital signs, and physical examination, refer to Sections [5.2.3](#) to [5.2.5](#). Genotyping will be performed in those volunteers whose genotypes have not been previously determined (for details, see Section [5.6.1](#)).

6.2.2 Treatment period

SRD Part:

Within 3 days before Day 1 of Visit 2 (but no later than Day -1), subjects will visit the trial site in the morning in an ambulatory fashion for assessment of safety laboratory parameters and orthostatic testing.

In the morning of Day 1 of Visit 2 subjects will be admitted to the trial site and drug screening and alcohol breath test will be performed. Each subject will receive one dose of trial medication (BI 474121 or placebo) at Visit 2.

Trial medication will be taken orally by each subject under direct supervision of the investigator or [redacted] designee. Details on treatments and procedures of administration are described in Section [4.1.4](#). After administration of investigational drug, subjects will remain under close medical surveillance for at least 48 h after investigational drug administration.

Subjects will then be allowed to leave the trial site on Day 3 after formal assessment and confirmation of their fitness by the Investigator or a designee.

On all other study days, subjects will be treated in an ambulatory fashion.

For details on time points and procedures for collection of plasma and urine samples for PK analysis, refer to [Flow Chart](#) and Section [5.3.2](#).

The safety measurements performed during the treatment period are specified in Section [5.3](#) of this protocol and in the Flow Chart. For details on times of all other trial procedures, refer to the Flow Chart. AEs and concomitant therapy will be assessed continuously from screening until the end of trial examination.

BA part:

In the BA part, each subject is expected to participate in 3 treatment periods. At least 1 week will separate drug administrations in the first and second treatment periods.

In the morning of Day 1 of Visit 2, 3 and 4 subjects will be admitted to the trial site and drug screening and alcohol breath test will be performed.

Subjects will receive one 2.5 mg or one 10 mg dose of BI 474121 as tablet or oral solution in each treatment period. Tablets will be administered with or without high-fat, high-calorie breakfast.

Trial medication will be taken orally by each subject under direct supervision of the investigator or [redacted] designee. Details on treatments and procedures of administration are described in Section 4.1.4. After administration of investigational drug, subjects will remain under close medical surveillance for at least 24 h. Subjects will then be allowed to leave the

Proprietary confidential information © 2020 Boehringer Ingelheim International GmbH or one or more of its affiliated companies

trial site on Day 2 after formal assessment and confirmation of their fitness by the Investigator or a designee. On all other study days, subjects will be treated in an ambulatory fashion.

For details on time points and procedures for collection of plasma samples for PK analysis, refer to [Flow Chart](#) and Section [5.3.2](#).

The safety measurements performed during the treatment period are specified in Section [5.3](#) of this protocol and in the Flow Chart. For details on times of all other trial procedures, refer to the Flow Chart. AEs and concomitant therapy will be assessed continuously from screening until the end of trial examination.

6.2.3 Follow-up period and trial completion

For AE assessment, laboratory tests, recording of ECG and vital signs, and physical examination during the follow-up period, see Sections [5.2.2](#) to [5.2.6](#).

Subjects who discontinue treatment before the end of the planned treatment period should undergo the EoTrial Visit.

All abnormal values (including laboratory parameters) that are assessed as clinically relevant by the investigator will be monitored using the appropriate tests until a return to a medically acceptable level is achieved. (S)AEs persisting after a subject's EoTrial Visit must be followed until they have resolved, have been sufficiently characterised, or no further information can be obtained.

7. STATISTICAL METHODS AND DETERMINATION OF SAMPLE SIZE

7.1 STATISTICAL DESIGN – MODEL

SRD part:

The main objectives of this trial will be assessed by calculating descriptive statistics for safety as well as for PK parameters, which will be compared between the treatment groups. Further analyses of these endpoints comprise the power model for assessment of dose proportionality.

BA part:

The main objectives of this part of the trial are to investigate the relative bioavailability of BI 474121 given as tablet under fed condition (Test 1, T1) compared with BI 474121 given as tablet under fasted condition (Test 2, T2) as well as the relative bioavailability of BI 474121 given as tablet under fasted condition (T2) compared with BI 474121 given as oral solution under fasted condition (Reference, R) on the basis of the primary and secondary pharmacokinetic endpoints, as listed in Section [2.1.2](#) and Section [2.1.3](#).

This part of the trial is designed to allow intra-subject comparisons and will be evaluated statistically by use of a linear model for logarithmically transformed PK endpoints.

7.2 NULL AND ALTERNATIVE HYPOTHESES

SRD part:

It is not planned to test any statistical hypotheses in this study.

Any confidence intervals computed are to be interpreted in the perspective of the exploratory character of the study; i.e., confidence intervals are considered as interval estimates for effects.

BA part:

The relative bioavailability of BI 474121 will be estimated by the ratios of the geometric means (T1/T2, T2/R), and their corresponding 2-sided 90% confidence intervals (CIs) will be provided. This method corresponds to the two one-sided t-test procedure, each at the 5% significance level. Since the main focus is on estimation and not testing, a formal hypothesis test and associated acceptance range is not specified.

7.3 PLANNED ANALYSES

Analysis sets

For both parts, statistical analyses will be based on the following analysis sets:

- Treated set (TS): The treated set includes all subjects who were randomised and treated with at least one dose of study drug. The treatment assignment will be

Proprietary confidential information © 2020 Boehringer Ingelheim International GmbH or one or more of its affiliated companies

determined based on the first treatment the subjects received. The treated set will be used for safety analyses.

- Pharmacokinetic parameter analysis set (PKS): This set includes all subjects in the treated set (TS) who provide at least one primary or secondary PK endpoint that was not excluded due to a protocol deviation relevant to the evaluation of PK or due to PK non-evaluability (as specified in the following subsection 'Pharmacokinetics'). Thus, a subject will be included in the PKS, even if he contributes only one PK parameter value for one period to the statistical assessment. Descriptive and model based analyses of PK parameters will be based on the PKS.

Adherence to the protocol will be assessed by the trial team. Important protocol deviation (iPD) categories will be specified in the Integrated Quality and Risk Management Plan, iPDs will be identified no later than in the Report Planning Meeting, and the iPD categories will be updated as needed.

Pharmacokinetics

The pharmacokinetic parameters listed in Section [2.1](#) and Section [2.2.2.2](#) for drug BI 474121 will be calculated according to the relevant SOP of the Sponsor ([001-MCS-36-472](#)).

Plasma and urine (in the SRD part of the trial) concentration data and parameters of a subject will be included in the statistical pharmacokinetic (PK) analyses if they are not flagged for exclusion due to a protocol deviation relevant to the evaluation of PK (to be decided no later than in the Report Planning Meeting) or due to PK non-evaluability (as revealed during data analysis, based on the criteria specified below). Exclusion of a subject's data will be documented in the CTR.

Relevant protocol deviations may be

- Incorrect trial medication taken, i.e. the subject received at least one dose of trial medication the subject was not assigned to
- Incorrect dose of trial medication taken
- Use of restricted medications

Plasma and urine (in the SRD part of the trial) concentrations and/or parameters of a subject will be considered as non-evaluable, if for example

- The subject experienced emesis that occurred at or before two times median t_{max} of the respective treatment (Median t_{max} is to be determined excluding the subjects experiencing emesis),
- Missing samples/concentration data at important phases of PK disposition curve.

In addition, plasma concentrations and/or parameters of a subject will be considered as non-evaluable in the BA part of the trial, if for example

- The subject experiences emesis at any time during the labelled dosing interval.
- A predose concentration is $>5\% C_{max}$ value of that subject

Proprietary confidential information © 2020 Boehringer Ingelheim International GmbH or one or more of its affiliated companies

Plasma and urine (in the SRD part of the trial) concentration data and parameters of a subject which is flagged for exclusion will be reported with its individual values but will not be included in the statistical analyses. Descriptive and inferential statistics of PK parameters will be based on the PKS.

Only concentration values within the validated concentration range and actual sampling times will be used for the calculation of pharmacokinetic parameters. Concentrations used in the pharmacokinetic calculations will be in the same format as in the bioanalytical report (that is to the same number of decimal places provided in the bioanalytical report).

7.3.1 Primary endpoint analyses

SRD part:

The primary endpoint as specified in Section [2.1.2](#) will be derived according to BI standards. The analysis will be based on the treated set (TS) and will be descriptive in nature.

BA part:

Primary analysis:

The secondary endpoints (refer to Section 2.1.2) will be calculated according to the BI Standard Operating Procedure (SOP) 'Standards and processes for analyses performed within Clinical Pharmacokinetics/ Pharmacodynamics' ([001-MCS-36-472](#)).

The statistical model used for the analysis of the secondary endpoints will be an analysis of variance (ANOVA) model on the logarithmic scale. That is, the PK endpoints will be logtransformed (natural logarithm) prior to fitting the ANOVA model. This model will include effects accounting for the following sources of variation: sequence, subjects within sequences, period and treatment. The effect 'subjects within sequences' will be considered as random, whereas the other effects will be considered as fixed. The model is described by the following equation:

$$y_{ijkm} = \mu + \zeta_i + s_{im} + \pi_j + \tau_k + e_{ijkm}, \text{ where}$$

y_{ijkm} = logarithm of response measured on subject m in sequence i receiving treatment k in period j,

μ = the overall mean,

ζ_i = the i^{th} sequence effect, $i = 1, \dots, 6$

s_{im} = the effect associated with the m^{th} subject in the i^{th} sequence,
 $m = 1, 2, \dots, n_i$

π_j = the j^{th} period effect, $j = 1, 2, 3$

τ_k = the k^{th} treatment effect, $k = 1, 2, 3$

Proprietary confidential information © 2020 Boehringer Ingelheim International GmbH or one or more of its affiliated companies

e_{ijkm} = the random error associated with the m^{th} subject in sequence i who received treatment k in period j .

where $s_{im} \sim N(0, \sigma_B^2)$ i.i.d., $e_{ijkm} \sim N(0, \sigma_W^2)$ i.i.d. and s_{im} , e_{ijkm} are independent random variables.

Point estimates for the ratios of the geometric means (T1/T2 and T2/R) for the primary endpoints (see Section 2.1) and their two-sided 90% confidence intervals (CIs) will be provided.

For each endpoint, the difference between the expected means for log(T)-log(R) will be estimated by the difference in the corresponding adjusted means (Least Squares Means). Additionally their two-sided 90% confidence intervals will be calculated based on the residual error from the ANOVA and quantiles from the t-distribution. These quantities will then be back-transformed to the original scale to provide the point estimate and 90% CIs for each endpoint.

7.3.2 Secondary endpoint analyses

SRD part:

The secondary endpoints (refer to Section 2.1.3) will be analysed descriptively. Analyses will be performed for the parent drug and for potential metabolites.

BA part:

The secondary endpoints (refer to Section 2.1.3) will be calculated according to the BI Standard Operating Procedure (SOP) 'Standards and processes for analyses performed within Clinical Pharmacokinetics/ Pharmacodynamics' ([001-MCS-36-472](#)) and will be assessed statistically using the same methods as described for the primary endpoints.

7.3.4 Safety analyses

Safety will be assessed as defined by the endpoints listed in Section [2.1.2](#) and [2.2.2](#) based on the treated set (TS). Safety analyses will be descriptive in nature and will be based on BI standards.

For all analyses the treatment actually administered (= treatment at onset) to the subject will be used (any deviations from the randomised treatment will be discussed in the minutes of the Report Planning Meeting).

Treatments will be compared in a descriptive way. The placebo group in the safety evaluation will consist of all subjects treated with placebo, regardless of the dose group in which they were treated. The test treatment groups will be compared to the placebo group in a descriptive

Proprietary confidential information © 2020 Boehringer Ingelheim International GmbH or one or more of its affiliated companies

way. Tabulations of frequencies/proportions will be used for the evaluation of categorical (qualitative) data, and tabulations of descriptive statistics will be used to analyse continuous (quantitative) data.

Measurements (such as ECGs, vital signs, or laboratory parameters) or AEs will be assigned to treatments (see Section 4.1) based on the actual treatment at the planned time of the measurement or on the recorded time of AE onset (concept of treatment-emergent AEs). Therefore, measurements planned or AEs recorded prior to intake of trial medication will be assigned to the screening period, those between the trial medication intake and end of REP (see Section 1.2.6) or next intake of study medication (BA part) will be assigned to the treatment period. Events occurring after the REP but prior to trial termination date will be assigned to 'follow-up'. These assignments including the corresponding time intervals will be defined in detail in the TSAP. Note that AEs occurring after the last per protocol contact but entered before database lock will be reported to Pharmacovigilance only and will not be captured in the trial database.

Additionally, further treatment intervals (called analysing treatments) may be defined in the TSAP in order to provide summary statistics for other than above periods, such as combined treatments, on-treatment totals, or periods without treatment effects (such as screening and post-study intervals).

Adverse events will be coded using the Medical Dictionary for Regulatory Activities (MedDRA). Frequency, severity, and causal relationship of AEs will be tabulated by treatment, system organ class and preferred term. SAEs, AESIs (see Section 5.2.6.1) and other significant AEs (according to ICH E3) will be listed separately.

Previous and concomitant therapies will be presented per treatment group without consideration of time intervals and treatment periods.

Laboratory data will be compared to their reference ranges. Values outside the reference range as well as possibly clinically significant values will be highlighted in the listings. Additionally, differences from baseline will be evaluated.

Vital signs or other safety-relevant data will be assessed with regard to possible on-treatment changes from baseline.

SRD part, only:

The ECG variables QT, HR, QTcF, QTcB, PR, QRS, and RR obtained from the centralised evaluation of 12-lead ECG recordings will be the basis for the derivation of quantitative and categorical ECG endpoints. These endpoints and their analyses will be described in the TSAP.

7.4 INTERIM ANALYSES

SRD part:

A preliminary analysis of PK parameters (AUC_{0-24} and C_{max} of BI 474121) provided as individual values and geometric means of the first cohort per dose level, will be performed for

- Dose level 1 before proceeding to dose level 3 (n+2)

Proprietary confidential information © 2020 Boehringer Ingelheim International GmbH or one or more of its affiliated companies

- Dose levels 3, 4, 5 and 6 (n) before proceeding to the next dose level 4, 5, 6, and 7 (n+1)

(Note: Data from the first cohorts of the above mentioned dose levels will be sufficient as long as the data from at least 2 subjects on active treatment were available.)

The pharmacokinetic parameters AUC_{0-24} and C_{max} for BI 474121 will be calculated according to the BI SOP 'Standards and processes for analyses performed within Clinical Pharmacokinetics/Pharmacodynamics' ([001-MCS-36-472](#)). The non-compartmental analysis will be performed using a validated software program such as Phoenix WinNonlin™ software (version 6.3 or higher, [REDACTED]) or SAS® Version 9.4 (or later version). A quality check of the preliminary data will be performed.

Available information on dose linearity from preceding dose groups will be considered when estimating C_{max} and AUC_{0-24} values to be expected for the next higher dose to be administered.

In contrast to the final PK calculations, the preliminary analysis will be based on planned sampling times rather than on actual times, regardless of whether actual times were within the time windows. Therefore, minor deviations may occur between preliminary and final results. The preliminary analysis will provide individual and mean concentration/effect-time profiles and summary statistics of individual values without subject identification information. The preliminary results will be distributed to the investigator and the trial team.

Depending on the results of available preliminary PK analyses and the tolerability and safety of the compound, changes to the dosing schedule (e.g., additional intermediate doses,) and additional PK/PD preliminary analysis may be performed if requested by the Trial Clinical Monitor, the investigator, or Trial Clinical Pharmacokineticist. Preliminary PK results will not be reported in the CTR.

No inferential statistical interim analysis is planned. However, after completion of each dose group the investigator (or his or her deputy) is allowed to postpone further dose progression until a preliminary analysis of the data has been performed.

BA part:

No interim analysis is planned.

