3. DESCRIPTION OF DESIGN AND TRIAL POPULATION

3.1 OVERALL TRIAL DESIGN AND PLAN

SRD part

This single-rising dose trial is designed as single-blind within dose groups, randomised, and placebo-controlled within parallel dose groups.

It is planned to include 56 healthy male subjects in this part of the trial. The subjects will be assigned to 7 groups consisting of 8 subjects per group; the groups will be dosed sequentially (see Table [3.1: 1](#)). The investigator is allowed to alter the scheduled dose groups (e.g., add low and/or intermediate dose groups) on the basis of experience gained during the study (for instance, based on preliminary PK data), provided the planned and approved highest dose is not exceeded. Thus, the actual number of subjects entered may be more than 56, but is not to exceed 72. Such changes may be implemented via non-substantial CTP amendments. The addition of further dose groups exceeding the already tested dose levels for the evaluation of safety findings is subject to a substantial CTP amendment requiring approval.

Within each dose group, 6 subjects will receive BI 474121 and 2 will receive placebo. Only one dose is tested within each dose group. For safety reasons, each dose group will consist of 3 cohorts.

The trial medication will be administered in the following order: For the first 4 subjects (cohort 1 and 2) the treatment order will be ‘active’ – ‘placebo’ – ‘active’ – ‘active’, while the following 4 subjects (cohort 3) will be randomised to 3x ‘active’ and 1x ‘placebo’

The second subject on active per dose group will be treated not earlier than 22 hours after the first subject on active (minimum time interval between 1st subject of cohort 1 [sentinel subject] and 1st of cohort 2). This is expected to be sufficient to detect relevant acute effects of BI 474121 in the sentinel subject based on an anticipated half-life of BI 474121 of approximately 19 hours prior to exposing more volunteers to BI 474121 at the respective dose level. In all cohorts, a time interval of at least 10 min will be maintained between dosings of individual subjects.

The dose groups to be evaluated are outlined in Table 3.1: 1 below.

Table 3.1: 1

Dose groups

Dose Group	1	2	3	4	5	6	7
Dose (mg)	0.25	1	2.5	5	10	20	40
Number of subjects	8	8	8	8	8	8	8
Subjects receiving placebo	2	2	2	2	2	2	2
Subjects receiving BI 474121	6	6	6	6	6	6	6

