The dose groups will be dosed consecutively in ascending order, and a time interval of at least 3 days will be maintained between the last drug administration to subjects in the previous dose group and the first drug administration to subjects in the subsequent dose group. Moreover, a time interval of at least 7 days will be maintained for DG 1 to 3 and 14 days for DG 4 to 7 between the first drug administration to subjects in the previous dose group and the first drug administration to subjects in the subsequent dose group. The decision to treat the next dose group will be based upon safety, tolerability and pharmacokinetic data (for details refer to Section [7.4](#)) of the preceding dose groups. The next dose group will only be treated if, in the opinion of the investigator, no safety concerns have arisen in the preceding dose groups (i.e. no dose-limiting events occurred), and if none of the pre-specified trial-specific stopping criteria have been met (refer to Section [3.3.4.2](#)).

A documented safety review must take place prior to each dose escalation. Furthermore, an unscheduled safety review meeting can be requested anytime by the Principal Investigator (or an authorised deputy) or the sponsor of the study (for instance, due to the occurrence of any unforeseen adverse events).

Although no formal Safety Review meeting will take place within a given dose group, safety will be continuously monitored during this trial, and an individual will only be dosed in the absence of any safety concern (i.e. no dose-limiting events occurred) and if none of the pre-specified trial-specific stopping criteria have been met (refer to Section 3.3.4.2).

At minimum, data from 4 subjects on active drug need to be available for escalation to a higher dose. For the minimum dataset with regards to preliminary PK data, see Section 7.4. The minimum data set for review consists of the following:

- AEs in the current and preceding dose groups up to at least 48 h post dosing, including clinically relevant findings from ancillary safety testing listed below (Note: AEs may be ongoing at the time of Safety Reviews and AE information may be subject to change prior to Database Lock)
- Results from 12-lead ECG and continuous ECG monitoring in the current and preceding dose groups up to at least 24 h (DG 1 to 3) or 48 h (DG 4 to 7) post dosing
- Vital signs and results from the orthostatic tests in the current and preceding dose groups up to at least 24 h post dosing

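### Before 40 mg is first dosed, the mandatory single-subject exposure stop need be checked in only 2 or 3 of the 6 active subjects at 20 mg

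*Protocol*

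**What the plan says.** Protocol 3.3.4.3 lists #6 among its mandatory criteria. Escalation stops if C_max or AUC_0-24 of at least one subject of a dose group exceeds the thresholds, or if the estimated gMean exposure is expected to exceed 657 nM or 6,201 nM*h. Section 1.3.3.2 makes enforcing the single-subject stop an aim of the preliminary PK analysis.

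Section 7.4 describes that analysis as "provided as individual values and geometric means of the first cohort per dose level". It is required for levels 3 to 6 before levels 4 to 7 (and for level 1 before level 3). A note adds that data from the first cohorts "will be sufficient as long as the data from at least 2 subjects on active treatment were available". For the projection to the next dose, "Available information on dose linearity from preceding dose groups will be considered". Further preliminary analyses may be requested and the investigator may postpone escalation; neither is required.

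Section 3.1 sets the cohorts. The first four subjects (cohorts 1 and 2) are dosed active, placebo, active, active, and "the following 4 subjects (cohort 3) will be randomised to 3x" active and one placebo. It also states "At minimum, data from 4 subjects on active drug need to be available for escalation to a higher dose", but continues: "For the minimum dataset with regards to preliminary PK data, see Section 7.4".

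**The concern.** The stop is written for any one of the six actives in a group, yet the PK that must be in hand before the next level can come from two or three of them. An active subject above the threshold at level n can be outside the required data when level n+1 starts, and no section sets a date by which his values must be checked. The four-active minimum in 3.1 does not help, because 3.1 sends the PK minimum to 7.4. What is at stake is whether a mandatory individual stop operates in time at the step where it is most likely to be needed.

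**Working it through.** **Inputs.** Thresholds 657 nM and 6,201 nM*h (3.3.4.3 #6). Predicted 40 mg exposure 285 nM and 2,850 nM*h (1.3.2.2). Six actives per group, three in cohorts 1 and 2 and three in cohort 3 (3.1). Assumed, because the documents give none: between-subject gCV of 30 to 70%, log-normal AUC_0-24, and a 40 mg projection equal to twice the gMean of the assayed 20 mg subjects.

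**The plan's own figures.** Linear scaling reproduces Table 1.3.3.1: 1. At 20 mg: 285 × 20/40 = 142.5 nM and 2,850 × 20/40 = 1,425 nM*h.

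**Who is checked.** Cohort 1 holds one active, so the floor of 2 must draw on cohort 2 as well; together they hold 3. Unchecked: 6 − 3 = 3, or 6 − 2 = 4 at the floor. If exactly one active exceeds, he is outside the required data with probability 3/6 = 50%, or 4/6 = 67%.

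**Distance to the AUC threshold at predicted exposure.** 5 mg: 6,201/356.2 = 17.4. 10 mg: 6,201/712.5 = 8.7. 20 mg: 6,201/1,425 = 4.35. The 20 mg result is the last that gates an escalation, so 20 to 40 mg is the tightest step.

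**Event.** At least one active at 20 mg is above 6,201, none of the n assayed is, and the projected 40 mg gMean is not above 6,201. With k the ratio of true to predicted exposure:

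- σ = √ln(1 + gCV²)
- p = 1 − Φ(ln(6,201/(1,425k))/σ)
- P(event) = P(no assayed value > 6,201 and 2 × gMean_n ≤ 6,201) × [1 − (1 − p)^(6−n)]

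The first factor is simulated and the second is exact.

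**Example, k = 2, gCV 50%, n = 3.** σ = √ln 1.25 = 0.472. ln(6,201/2,850) = 0.777. p = 1 − Φ(1.646) = 0.0499. First factor 0.599; second 1 − 0.9501³ = 0.142; product 8.5%. For n = 2: 0.594 × 0.185 = 11.0%. At least one of the six exceeds in 1 − 0.9501⁶ = 26.5% of groups, so the required checks miss about a third of these and still permit 40 mg.

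| Exposure vs prediction | n assayed | gCV 30% | 40% | 50% | 60% | 70% |
|---|---|---|---|---|---|---|
| 1 | 3 | 0.0% | 0.02% | 0.3% | 1.2% | 2.8% |
| 1.5 | 3 | 0.04% | 0.8% | 3.2% | 6.7% | 10.4% |
| 2 | 3 | 0.8% | 4.1% | 8.5% | 12.5% | 15.5% |
| 2 | 2 | 1.1% | 5.2% | 11.0% | 16.4% | 20.6% |
| any | 6 | 0% | 0% | 0% | 0% | 0% |

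**Effect of the gMean rule.** At k = 2 the true 40 mg gMean is 5,700, which is 92% of the threshold. With n = 3 the gMean rule alone blocks 40 mg in 31 to 41% of cases over the gCV range. It removes part of the risk, not all.

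**Both measures.** Applying #6 and the gMean rule to C_max and AUC_0-24 together (assumed log-scale correlation 0.5 to 0.8) at k = 2, n = 3, gCV 50% gives 10.1 to 10.4% in place of 8.5%.

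**Lower steps, k = 2, n = 3, gCV 50%.** 10 to 20 mg: 0.3%. 5 to 10 mg: about 0.001%.

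**The case against.** The case for leaving the plan alone has several parts.

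- *The size rests on assumptions.* At predicted exposure and n = 3 the chance is at most 0.3% up to a gCV of 50%. The larger figures need exposure well above prediction together with substantial variability, and the documents support neither specifically. This stands, and it limits the weight of the point.
- *The subject who was missed has had his only dose.* The 40 mg group has its own protection: the gMean projection, a safety review with at least 4 actives, and a sentinel dosed at least 22 hours before the second active. Under 3.1 "an individual will only be dosed in the absence of any safety concern" and only if no stopping criterion has been met, so a late 20 mg result would still halt the remaining 40 mg subjects. This also stands. The probabilities above count the event even if only the sentinel had been dosed by then. But no such rule can act on a sample that has not been assayed.
- *The choice is deliberate.* Section 3.1 refers the PK minimum to 7.4, and the team may look at more data. True, but an option does not secure a mandatory stop.
- *Operational detail may sit elsewhere.* SAP Section 8 ties release of SRD treatment information to completion of dose groups under a logistics plan that is not public. This is ambiguous and does not show that PK from six actives is required.

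A reader might infer that healthy subjects would be exposed to harmful levels. The documents do not support that. Section 1.4.3 calls the limit precautionary, and by 1.3.2.2 rat NOAEL exposure is 4.2 × 285 = 1,197 nM and 4.0 × 2,850 = 11,400 nM*h, so the thresholds lie at about 55% and 54% of it. A reader might also infer that every escalation step needs the change; the figures for the lower steps do not bear that out. Nor does 7.4 name cohorts 1 and 2: that is inferred from the plural in its note.

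**Conclusion.** The gap is in the text and holds whatever the variability: 7.4 does not require the check in #6 for 3 of the 6 actives (4 at the floor) before the next level is first dosed. Its practical weight is confined to the 20 to 40 mg step. With a gCV of 50% and n = 3, the chance of an unseen exceeder with 40 mg still permitted runs from 0.3% at predicted exposure to 8.5% at twice prediction; over gCVs of 30 to 70% the twice-prediction range is 0.8 to 15.5%. These figures assume log-normal AUC and linear projection, and they take the thresholds in #6 as operative; the section defining the maximum acceptable exposure (1.3.2.1) is not in the public text. This is a flaw in how the plan enforces its own precautionary stop, worth a short amendment for that one step.

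**What to change.** In Section 7.4, for dose level 6 before dose level 7, add wording such as:

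*Before the first 40 mg dose, individual C_max and AUC_0-24 of all active subjects dosed at 20 mg who have evaluable samples are compared with the thresholds in 3.3.4.3 #6. A sample collected but not yet assayed does not count as unavailable. Dropouts and subjects with non-evaluable PK are documented in the Safety Review minutes and do not block escalation, provided at least the 4 active subjects required by Section 3.1 have PK.*

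Extending this to levels 4 and 5 is optional.

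**Cost.** No added blood or visits; the samples are already scheduled. Bioanalysis must be faster (the documents do not state turnaround), and the 40 mg group may start some days later. The 14-day first-to-first interval applies here. If cohorts run on consecutive days (an assumption, since 22 hours is only a minimum), the last 24-hour sample falls on Day 4 and 40 mg starts on Day 15 at the earliest, leaving 15 − 4 = 11 days. Whatever the spacing, Section 3.1 guarantees a gap: "a time interval of at least 3 days will be maintained between the last drug administration to subjects in the previous dose group", counted to the opening dose of the next group. That leaves at least 3 − 1 = 2 days after the last 24-hour sample.
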